7.6. Investigational Product Compliance

Luspatercept will be administered as a subcutaneous injection at the clinical site by the study staff. Monitoring for subject compliance with the treatment regimen is therefore unnecessary.

The investigator or designee is responsible for accounting for all IP that is administered during the course of the study.

Accurate recording of all IP administration will be made in the appropriate section of the subject's eCRF and source documents.

8. CONCOMITANT MEDICATIONS AND PROCEDURES

Over the course of this study, additional medications may be required to manage aspects of the disease state of the subjects, including side effects from trial treatments or disease progression. Supportive care may be administered at the discretion of the investigator.

All prior/ concomitant medications, used 8 weeks prior to W1D1 until 42 days after the last dose of IP (or until the EOT Visit, whichever occurs later), must be reported on the eCRF. All prior procedures within the 8 weeks prior to W1D1 as well as concomitant procedures (including transfusions) will be recorded on the appropriate eCRF(s).

Prior anticancer treatments should be recorded on the appropriate eCRF(s) regardless of treatment discontinuation/procedure date.

Prior ESAs and G-CSF/GM-CSF should be recorded on the appropriate eCRF(s) regardless of treatment discontinuation date.

If a subject requires treatment with any new medications that are specifically excluded in Section 8.2, the subject will be discontinued from treatment and should complete the EOT visit and enter the Post-Treatment Follow-up Period of the study. The investigator should consult the medical monitor regarding any questions about whether a new medication or dosage of existing medication would require the subject to discontinue from the study.

For information regarding other drugs that may interact with IP and affect its metabolism, pharmacokinetics, or excretion, please see the IB and/or package insert.

8.1. Permitted Concomitant Medications and Procedures

8.1.1. RBC Transfusions

Concurrent treatment for anemia with blood transfusions is allowed, at the discretion of the investigator, for low hemoglobin levels, symptoms associated with anemia (eg, shortness of breath, fatigue etc.) or comorbidity.

For any RBC transfusions received during the study, hemoglobin values just prior to transfusion will be collected. Please refer to Section 6.4.1 for details on required data collection.

8.1.2. Corticosteroids

Concurrent systemic corticosteroids used for medical conditions other than MDS is allowed provided the subject is on a stable or decreasing dose for \geq 1 week prior to W1D1. Use of topical steroids is permitted. Occasional use of corticosteroids before transfusions to prevent allergic reactions is permitted.

8.1.3. Attenuated Vaccines

Administration of attenuated vaccines (eg, influenza vaccine) is allowed if clinically indicated, per investigator discretion with the exception of a live COVID-19 vaccine.

8.1.4. Phlebotomy

Phlebotomy may be performed for emergency/urgency if excessively high Hgb levels occur.

8.2. Prohibited Concomitant Medications and Procedures

Best supportive care for this study specifically excludes cancer surgery, immunotherapy, biologic therapy, radiotherapy, and systemic chemotherapy where the goal is to eradicate or slow the progression of the disease.

The following concomitant medications are specifically excluded during the course of the study:

- ESAs and other RBC hematopoietic growth factors (eg, Interleukin-3)
- Granulocyte colony stimulating factors (ie, G-CSF, GM-CSF), except in cases of neutropenic fever or as clinically indicated per product label.
- Cytotoxic, chemotherapeutic, targeted or investigational agents/therapies
- Azacitidine, decitabine or other hypomethylating agents
- Lenalidomide, thalidomide and other immunomodulating drugs (IMiDs)
- Hydroxyurea, anagrelide
- Androgens, unless to treat hypogonadism
- Oral retinoids
- Arsenic trioxide
- Interferon and interleukins

Administration of a live COVID-19 vaccine is prohibited within 4 weeks prior to randomization. Live COVID-19 vaccines should not be used during the study, including the treatment period and until 42 days following the last dose of IP.

8.3. Required Concomitant Medications and Procedures

Not applicable.

9. STATISTICAL CONSIDERATIONS

9.1. Overview

This is a Phase 2, multicenter, single-arm study. The primary objective of the study is to evaluate HI-E per IWG ([Cheson, 2006](#)) for the treatment of anemia due to IPSS-R very low, low, or intermediate risk MDS in Japanese subjects who are not requiring RBC transfusion.

The design of the study, including the proposed targeted subject population, study endpoints, and statistical plan, is discussed below.

9.2. Study Population Definitions

Study populations to be analyzed are defined as follows:

Intent-to-treat (ITT): The ITT population will consist of all enrolled subjects regardless of whether or not the subject received IP.

Efficacy Evaluable (EE): The EE population will consist of 1) all subjects who received at least one dose of IP and 2) have at least two hemoglobin assessments \geq 8 weeks apart post-treatment.

Safety: The safety population will consist of all subjects who were enrolled and received at least one dose of IP. Statistical methods to handle missing data will be described in the statistical analysis plan (SAP). The SAP will describe any predefined rules for including/excluding any subjects with data from any analyses (eg, time windows, visit by visit analysis, endpoint analysis, protocol violation).

9.3. Sample Size and Power Considerations

For the primary efficacy endpoint, HI-E, the sample size is based on one sample binomial exact test. The null hypothesis to be tested is that the proportion of subjects achieving HI-E (defined as ≥ 1.5 g/dL increase in Hgb over any consecutive 56-day period in the absence of RBC transfusions) is $\leq 10\%$; the alternative hypothesis is that the proportion of subjects achieving HI-E is $> 10\%$. With these hypotheses, a sample size of 20 subjects are required with a power of 95% at a one-sided 0.025 alpha level if the expected proportion is 45%. This criterion requires that the lower limit of the 95% confidence intervals for the HI-E rate is greater than 10%.

The selection of a null hypothesis of 10% HI-E rate is based on the results of ARCADE Phase 3 study of darbepoetin, where the proportion of subjects achieving HI-E was reported as 14.7% (95% CI: 8%–25%) (11/75) ([Platzbecker, 2017c](#)). Based on the lower limit of 95% CI, the null hypothesis is assumed as 10%. The expected proportion of 45% HI-E rate is based on the preliminary efficacy observed with luspatercept in the ex-Japan Phase 2 study ([Platzbecker, 2017a](#)). In the study, HI-E rate was 63% (95% CI: 48%–76%) (32/51 evaluable). Based on the lower limit of 95% CI, the expected proportion is assumed as 45%.

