1.1.1.1. Erythropoiesis Stimulating Agents

The use of ESAs (ie, recombinant erythropoietin [EPO] or darbepoetin [DAR]) is the standard of care for low and intermediate IPSS risk patients with symptomatic anemia and an endogenous serum erythropoietin (sEPO) level < 500 U/L, and is recommended by European, United States (US), and Japanese treatment guidelines. The use of granulocyte-colony stimulating factor (G-CSF) may be employed as needed but is not required, although in some cases it may further improve the efficacy of the ESA ([NCCN, 2017](#); [ESMO, 2014](#) [[Fenaux, 2014](#)]; [ELN, 2014](#) [[Malcovati, 2013](#)]; [JSH, 2013](#)).

The European and Japanese guidance also recommends the use of ESAs for patients who have a low RBC transfusion burden (< 2 units/month) and/or an endogenous sEPO levels \leq 500 U/L ([ESMO, 2014](#) [[Fenaux, 2014](#)]; [ELN, 2014](#) [[Malcovati, 2013](#)]; [JSH, 2013](#)). However, major favorable prognostic factors for response to ESAs are a low or no RBC transfusion requirement (< 2 units/month) and an endogenous sEPO level < 500 U/L ([Fenaux, 2013](#)). Responses to ESAs are best in patients with low endogenous levels (eg, < 500 U/L) of EPO, normal blast counts and lower IPSS/WHO Prognostic Scoring System (WPSS) scores ([Hellstrom-Lindberg, 2003](#); [Santini, 2011](#)).

Efficacy of ESAs in lower risk MDS patients have recently been demonstrated in 2 Phase 3 studies:

In the EPOANE3021 Phase 3 study, a total of 130 subjects with IPSS low or int-1 risk MDS and anemia \leq 10 g/dL with a requirement of RBC transfusion \leq 4 units/8 weeks and an endogenous sEPO level < 500 U/L, were randomized 2:1 to receive either epoetin alfa or matching placebo. Subjects were stratified by endogenous sEPO level (sEPO < 200 U/L versus sEPO \geq 200 U/L) and prior transfusion status at screening (yes versus no).

In the modified intent-to-treat (ITT) analysis 2/45 (4.4%) subjects in the placebo group achieved the primary endpoint of IWG 2006 erythroid response versus 27/85 (31.8%) in the epoetin alfa group ($p < 0.001$). All of the responding subjects were in the stratum with endogenous sEPO < 200 U/L during screening. In that stratum, 20/40 (50%) subjects without prior transfusions demonstrated erythroid response during the first 24 weeks, compared with 7/31

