(22.6%) subjects with prior transfusions (2 subjects with prior transfusion reached the primary endpoint based on reduction of RBC units transfused by an absolute number of at least 4 units every 8 weeks compared to the 8 weeks prior to baseline). The median duration of erythroid response in the epoetin alfa group was 197 days. The percentage of subjects who were transfused in the epoetin alfa group decreased from 51.8% in the 8 weeks prior to baseline to 24.7% between weeks 16 and 24, compared to the placebo group which had an increase in transfusion rate from 48.9% to 54.1% over the same time periods ([Fenaux, 2016](#); [Fenaux, 2018a](#)). In an additional post-hoc analysis conducted by the response review committee with modified IWG 2006 criteria an erythroid response rate of 39/85 (45.9%) in the epoetin alfa group was estimated ([Fenaux, 2017](#)); [Fenaux, 2018a](#)).

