In the ARCADE Phase 3 study, a total of 146 subject with IPSS low or int-1 risk MDS and anemia \leq 10 g/dL, requirement of RBC transfusion $<$ 4 units/8 weeks, and an endogenous sEPO level \leq 500 U/L were randomized 2:1 to receive either darbepoetin alfa (DAR) or matching placebo (PBO). In the ITT analysis, 29 (59.2%) subjects in the PBO group achieved the primary endpoint (percentage of participants with at least 1 RBC transfusion during the double-blind treatment period: weeks 5 to 24) versus 35 (36.1%) subjects in the DAR group ($p = 0.008$). Transfusion rates were less with lower baseline sEPO for darbepoetin alfa (\leq 100 U/L: 23%, $>$ 100 U/L: 57%, 95% confidence interval non-overlapping) but not placebo. The proportion achieving the hematologic improvement – erythroid response (HI-E), which was defined as a \geq 1.5 g/dL increase from baseline in hemoglobin with a mean rise of \geq 1.5 g/dL for 8 weeks without transfusions as per IWG 2006 criteria, was significantly increased with DAR versus PBO; DAR:14.7% (11 of 75 evaluable) versus PBO:0% (0 of 35 evaluable), $p = 0.016$. All subjects with HI-E ($n=11$) in the double-blind period had baseline sEPO \leq 100 U/L and 10/11 had no transfusions in the 16 weeks before randomization (none had transfusions in the 8 weeks before). The mean duration of response was 235 (21 days standard error) days. It should be noted, however, that the primary endpoint was switched during the course of the study. Before unblinding and while enrollment was ongoing, transfusion incidence from weeks 5 to 24 became the primary endpoint and HI-E a secondary endpoint ([Platzbecker, 2017c](#)).

In Japan, DAR was approved in 2014 regardless of patients' sEPO levels based on the results of a Phase 2 study conducted in 50 patients in Japan and Korea. However, the study only included the subjects with EPO $<$ 500 U/L ([Jang, 2015](#)) and JSH Guideline recommends DAR to patients who have low serum EPO ($<$ 500 mU/mL) ([JSH, 2013](#)).

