1.3.2.1. Rationale for the Study Population

This study targets subjects who have symptomatic anemia accompanied by Hgb concentration < 10.0 g/dL and are not requiring RBC transfusion to evaluate the PD and efficacy in IPSS-R very low- to intermediate-risk MDS subjects who are not influenced by RBC transfusions. The subjects will be ESAs naïve or previously used ESAs but not administered ESAs within 8 weeks prior to W1D1 to washout the effects of ESAs.

The IPSS-R classification has been chosen to define this Phase 2 study population because this classification provides better discrimination of MDS progression risk factors compared with the original IPSS ([Greenberg, 1997](#)) for evaluating clinical outcomes (survival duration and time to progression of AML) for MDS subjects ([Greenberg, 2012](#)). For the purpose of this study, subjects with IPSS-R very-low, low and intermediate risk will be referred to as lower risk MDS.

Subjects in the lower risk groups often become dependent on frequent RBC transfusions, which leads to decreased HRQoL and increased morbidity and mortality ([Hellstrom-Lindberg, 2003](#); [Malcovati, 2005](#)). Thus, the therapeutic goal in this subject population is to increase Hgb level and prevent from becoming RBC-TD, which is evaluated in this study.

Subjects can be enrolled to this study regardless of their baseline endogenous EPO level. According to the recent published data ([Suzuki, 2015](#)), the endogenous EPO level has a strong correlation with transfusion dependency, and a significantly larger proportion of patients showed serum EPO levels higher than 500 U/L in TD patients (68 % of TD versus 14 % of TI patients). Since the target population of the study is lower risk MDS subjects who are not requiring RBC transfusion, it is anticipated that most of the patients have EPO levels < 500 U/L. However, there is an unmet need for patients with EPO level \geq 500 U/L in Japan because the use of ESAs are not recommended for these patients, and therefore, it is allowed to enroll subjects with EPO level \geq 500 U/L. As described before, in the preliminary ex-Japan Phase 2 study results for

luspatercept, HI-E rates are 76% (19/25) (baseline endogenous sEPO < 200 U/L), 58% (7/12) (200-500 U/L), and 43% (6/14) (> 500 U/L) and rates of RBC-TI of 53% (10/19) (< 200 U/L), 44% (4/9) (200-500 U/L), and 14% (2/14) (> 500 U/L) ([Platzbecker, 2017a](#)).

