In the ARCADE Phase 3 study for DAR, HI-E as per IWG 2006 criteria was defined as ≥ 1.5 g/dL increase from baseline in Hgb with a mean rise of ≥ 1.5 g/dL for 8 weeks without transfusions. To ensure better comparison of efficacy data between luspatercept and DAR, modified HI-E (mHI-E) per IWG 2006 criteria defined as ≥ 1.5 g/dL mean increase in Hgb compared to baseline over any consecutive 56-day period in the absence of RBC transfusions is added in the secondary endpoints.

Other secondary objectives include evaluation of efficacy (eg, time to and duration of HI-E and mHI-E, duration of transfusion independence; HRQoL) as well as safety and PK. Safety is assessed by evaluating adverse events and laboratory data. Adverse events and abnormal laboratory value severity will be graded using version 4.03 of the National Cancer Institute Common Terminology Criteria for Adverse Events (NCI CTCAE). Biomarkers will also be measured as exploratory endpoints.

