4.2. Inclusion Criteria

Subjects must satisfy the following criteria to be enrolled in the study:

1. Subject is \geq 20 years of age the time of signing the informed consent form (ICF)
2. Subject must understand and voluntarily sign an ICF prior to any study-related assessments/procedures being conducted.
3. Subject is willing and able to adhere to the study visit schedule and other protocol requirements.
4. Subject has a documented diagnosis of MDS according to WHO 2016 classification (Section 6.1.1, Appendix B) that meets IPSS-R classification (Greenberg, 2012) of very low, low, or intermediate risk disease, and:
 - < 5% blasts in bone marrow
5. Subject has symptomatic anemia with mean Hgb concentration < 10.0 g/dL from 2 measurements (one performed within 1 day prior to W1D1 and the other performed 7 to 35 days prior to W1D1) that does not require RBC transfusion. If more than one measurement exists in the period of 7 to 35 days prior to W1D1, the most recent value will be used.
6. Subject must be TI, as documented by the following criteria:
 - No RBC transfusion administered within 16 weeks prior to W1D1 (except transfusions due to blood loss or infection that occurred between 16 and 8 weeks prior to W1D1)
7. Subject has Eastern Cooperative Oncology Group (ECOG) score of 0, 1, or 2
8. Females of childbearing potential (FCBP), defined as a sexually mature woman who: 1) has achieved menarche at some point, 2) not undergone a hysterectomy or bilateral oophorectomy, or 3) has not been naturally postmenopausal (amenorrhea following cancer therapy or amenorrhea due to other medical reasons does not rule out childbearing potential) for at least 24 consecutive months (ie, has had menses at any time in the preceding 24 consecutive months), must:
 - Have two negative pregnancy tests as verified by the investigator prior to starting study therapy (unless the screening pregnancy test was done within 72 hours of W1D1). Refer to Section 6.1.14 for additional details. She must agree to ongoing pregnancy testing during the course of the study, and after end of study treatment. This applies even if the subject practices true abstinence¹ from heterosexual contact.

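### Does a darbepoetin rate from a partly transfused population undermine the 10% null or the purpose of mHI-E?

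*Combined protocol and SAP*

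**What the plan says.** Section 9.3 tests H0: HI-E rate at or below 10% with 20 subjects, one-sided alpha 0.025 and an expected rate of 45%. On the null it says: "The selection of a null hypothesis of 10% HI-E rate is based on the results of ARCADE Phase 3 study of darbepoetin". The figure cited is 14.7% (11/75), 95% CI 8% to 25%, and 10% was chosen with reference to the lower limit.

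Section 1.3.2.2 gives the reason for the modified endpoint: "To ensure better comparison of efficacy data between luspatercept and DAR, modified HI-E (mHI-E) per IWG 2006 criteria" was added to the secondary endpoints. Section 9.6.2 analyses secondary variables descriptively unless otherwise specified, in both the ITT and efficacy evaluable populations. It names no test against darbepoetin.

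Section 1.1.1.1 describes the darbepoetin Phase 3 study. Subjects could need fewer than 4 RBC units per 8 weeks and had sEPO of at most 500 U/L. The response was a mean rise, reported as "DAR:14.7% (11 of 75 evaluable) versus PBO:0% (0 of 35 evaluable". Of the 11 responders, "10/11 had no transfusions in the 16 weeks before randomization (none had transfusions in the 8 weeks before", and all had sEPO at or below 100 U/L.

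Section 4.2 of this trial requires: "No RBC transfusion administered within 16 weeks prior to W1D1", with an exception for blood loss or infection between weeks 16 and 8. There is no sEPO limit, and earlier ESA use is allowed after an 8-week washout.

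**The concern.** mHI-E brings the response definition into line with the darbepoetin study but not the population. Every recently transfused subject among the 75 adds to the denominator and contributes no responder, and this trial excludes such subjects. Taken alone, that makes 11/75 too low as a darbepoetin rate for the people enrolled here.

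The epoetin alfa Phase 3 study in Section 1.1.1.1 shows the same pattern among subjects with sEPO below 200 U/L: "In that stratum, 20/40 (50%) subjects without prior transfusions demonstrated erythroid response during the first 24 weeks", against 7/31 (22.6%) with prior transfusions.

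If 11/75 were used uncritically, luspatercept could appear better than darbepoetin partly because of who was enrolled. Rejecting a 10% null could also be misread as beating an active drug. Sections 9.3, 1.3.2.2 and 9.6.2 do not mention the mismatch.

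**Working it through.** **1. The plan's own figures.** Exact binomial, n = 20, p0 = 0.10:

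- P(X ≥ 5) = 0.0432, above 0.025.
- P(X ≥ 6) = 0.0113, so the rule is at least 6 responders.
- Power at 45% is P(X ≥ 6) = 0.9447, which matches the stated 95% within rounding.
- Clopper-Pearson for 11/75 is 7.6% to 24.7%, matching the stated 8% to 25%.

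**2. Effect of transfusion mix alone.** Let f be the transfusion-free share of the 75. With no responders among those transfused in the prior 8 weeks, the transfusion-free rate is 11/(75f). The protocol does not give f, so the values below are assumptions. The only related figure is from the epoetin arm, whose transfused share "decreased from 51.8% in the 8 weeks prior to baseline": 44 of 85 transfused, 41 of 85 not, f = 0.48.

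| f (assumed) | 11/(75f) |
|---|---|
| 1.0 | 14.7% |
| 0.8 | 11/60 = 18.3% |
| 0.6 | 11/45 = 24.4% |
| 0.48 | 11/36 = 30.6% |
| 0.4 | 11/30 = 36.7% |

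A drug with a true rate of 18.3% to 36.7% would reject 10% with probability 0.14 to 0.80. Those rejections are correct, because such rates do exceed 10%.

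**3. Effects in the other direction.**

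*Denominator.* Section 1.1.1.1 gives 35 darbepoetin subjects as 36.1%, so the arm had 35/0.361 ≈ 97. The placebo arm is 29/0.592 ≈ 49, and 97 + 49 = 146, the stated total. Counting the 22 non-evaluable subjects as non-responders, as an ITT analysis would, gives 11/97 = 11.3%, a factor of 75/97 = 0.77.

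*sEPO above 500 U/L.* Section 1.3.2.1 gives the share above 500 U/L as "68 % of TD versus 14 % of TI patients". With no ESA response in that 14%, the factor is 0.86. This captures only the part above 500 U/L. All 11 responders were at or below 100 U/L, and the protocol gives no share above 100 U/L for either population, so the full sEPO effect cannot be calculated.

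*Prior ESA use.* Subjects for whom an ESA has already failed can enrol here. Their share is not given.

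**4. Putting them together.** With f now taken as the transfusion-free share of the 97:

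| f (assumed) | 11/(97f) | × 0.86 |
|---|---|---|
| 0.8 | 14.2% | 12.2% |
| 0.6 | 18.9% | 16.3% |
| 0.48 | 23.6% | 20.3% |
| 0.4 | 28.4% | 24.4% |

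The adjusted rate equals 14.7% when f = 0.86 on the evaluable denominator, but when f = 0.77 × 0.86 = 0.66 on the ITT denominator. Above that value 11/75 is too high as a comparator, below it too low. This is before any allowance for prior ESA failure or for sEPO between 100 and 500 U/L, both of which lower the matched rate further.

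**5. Precision.** With 20 subjects, 6 responders give 30% (95% CI 11.9% to 54.3%) and 9 give 45% (23.1% to 68.5%). A descriptive reading at this size cannot separate most of the rates in these tables.

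**6. Is 10% reasonable as an activity threshold?** The placebo response rates in Section 1.1.1.1 are 0/35 and 2/45 (4.4%). The second arm had 48.9% transfused, about 22 of 45, leaving 23. Even if both responders were untransfused, 2/23 = 8.7%, still under 10%. With two events this is only a rough check, but it gives no sign that the transfusion mix has made 10% too easy as a no-activity threshold.

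**The case for a change.** The case for acting is that the mismatch is visible in the protocol's own text and that Section 1.3.2.2 makes comparison with darbepoetin the purpose of mHI-E. A descriptive comparison still needs like populations. The remedy would cost little: a sentence or two in Section 9.3, a comparator note in Section 9.6.2 and a subgroup cut in Section 9.9.4.

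Part of this stands. The populations differ, and the transfusion mix by itself does lower 11/75. If the transfusion-free share were near the epoetin study's 0.48, the matched rate would exceed 14.7% on either denominator in the tables.

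The rest does not carry through. The 0.48 comes from another study with a different transfusion cap and a modified ITT set. The net direction therefore depends on quantities the protocol does not contain. Significance tests of 9/20 against adjusted rates would examine a comparison the protocol never proposes.

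The remedies add little. A note in Section 9.3 would mostly repeat Section 1.1.1.1, which already gives the transfusion limit, evaluable denominator, mean-rise definition and responders' history. A matched comparator needs a count from outside the protocol. Cuts by prior ESA use or a lower sEPO threshold are already possible under the other baseline characteristics in Section 9.9.4, and in 20 subjects would be very imprecise.

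**Conclusion.** The population mismatch is real, but no change to the plan follows. The null, alpha, sample size and rejection rule (6 of 20, size 0.0113, power 94.5%) are sound for the question asked, which is whether luspatercept is active above 10%. No superiority to darbepoetin is claimed or tested, and mHI-E is descriptive.

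How far 11/75 misstates a matched darbepoetin rate cannot be settled from the protocol. Under the assumed transfusion-free shares of 0.4 to 0.8, the matched rate runs from 12.2% (ITT denominator, sEPO factor applied) to 36.7% (evaluable denominator, transfusion mix only). That range lies on both sides of 14.7%, with prior ESA failure and sEPO between 100 and 500 U/L still unquantified. It also assumes that the non-evaluable subjects did not respond and that sEPO above 500 U/L means no ESA response.

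The remaining point concerns interpretation at reporting: rejecting 10% shows activity, not a rate above darbepoetin's, and mHI-E set beside 11/75 is a cross-study reading of differently selected subjects. An analyst can say so from Section 1.1.1.1 as written.
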